COVER PAGE FOR PROTOCOL AND STATISTICAL ANALYSIS PLAN

Official Study Title: Use of Amiodarone in Atrial Fibrillation Associated With Severe Sepsis or Septic Shock

NCT number: NCT02668432

IRB Approval Date: 02.01.16

Unique Protocol ID: HSC2016084H

Protocol Template Form

Item 1 UTHSCSA	HSC20150864H
Tracking Number	

Provide a succinct and accurate description of the proposed research. State the purpose/aims. Describe concisely the research design and methods for achieving the stated goals. This section should be understandable to all members of the IRB, scientific and non-scientific.
DO NOT EXCEED THE SPACE PROVIDED.

Purpose/Objectives: Severe sepsis and septic shock are a common cause of new onset atrial fibrillation (NOAF) in the intensive care unit. Development of NOAF in this setting can prolong length of stay and increase mortality. Amiodarone is the most commonly used agent used in this setting to control rate and rhythm. However, limited data exist detailing appropriate dosing in this setting. The primary objective of this study is to evaluate two amiodarone dosing strategies, a full loading dose versus a partial loading dose, in patients with new-onset atrial fibrillation (AF) due to severe sepsis or septic shock to assess the mean heart rate every 6 hours after initiation of amiodarone infusion to day 7 or death.

Research Design/Plan: Consecutive patients admitted to the medical or cardiac intensive care unit at University Hospital with NOAF in the setting of severe sepsis or septic shock will be screened for study inclusion. Data will be collected and stored using Microsoft Excel or Access and analyzed with JMP 12.0 and SPSS.

Methods: Patients aged 18 years or older who develop new-onset atrial fibrillation in the setting of severe sepsis or septic shock and in whom the medical team deems appropriate to initiate amiodarone therapy in will be considered for study inclusion. Patients will be randomized to a full loading dose (\geq 5g IV or \geq 10g PO +/- 20%) or a partial loading dose (<4g IV or < 8g PO).

Clinical Relevance: With ICU LOS and mortality being twice as high in NOAF with sepsis as compared to septic patients without NOAF, we ultimately aim to identify a management strategy that may minimize this morbidity and mortality while also minimizing exposure to a drug that may cause serious adverse effects.

Item 3 Background	
Describe past experimental and/or clinical findings leading to the formulation of your study. For research involving unapproved drugs, describe animal and human studies. For research that involves approved drugs or devices, describe the FDA approved uses of this drug/device in relation to your protocol.	Severe sepsis and septic shock, together, account for 2.9% and 10% of total hospital and intensive care unit (ICU) admissions in North America, respectively. An estimated 750,000 cases of sepsis occur annually in the United States, with a mortality rate of approximately 30%. ¹ In the setting of new onset atrial fibrillation (NOAF), which affects between 7% and 30% of patients hospitalized with sepsis, the mortality rate is closer to 70-80% and the ICU length of stay is doubled. ²⁻⁴ In sepsis, the causality has been widely disputed, and some even question whether atrial fibrillation (AF) may simply be a marker of illness severity, rather than an independent contributor to mortality. ^{2,5,6}
	AF is a multifactorial disease that can affect those with structural cardiac abnormalities and structurally normal hearts alike. The cascade of events that occur in the critically ill septic patient, including tissue hypoperfusion, organ dysfunction, inflammation, hypoxemia, electrolyte disturbances, hormonal dysregulation, fluctuations in autonomic tone, fluid imbalances, and catecholamine requirements, have each been implicated in the quest to identify the cause of NOAF. ^{7,8}
	To date, no studies have assessed what implications conversion back to NSR from NOAF may have on clinical outcomes. The approach to management of AF and conversion to NSR varies. Outside of sepsis, in patients with AF and hemodynamic instability, direct current cardioversion (DCC) is preferred because of its high acute efficacy of 67 to 94%.(7) However, because the trigger for NOAF in the septic patient lies somewhere in the pathophysiology of sepsis, sustainable efficacy of DCC is debatable, especially without identification and removal of underlying triggers.(6,8) Studies of NOAF in septic patients have shown that DCC with concomitant or subsequent pharmacologic therapy is often necessary; however, the best pharmacotherapeutic approach is a point of discussion. Rate control with beta blockers may exacerbate hypotension, and digoxin use is unsuccessful due to the absence of vagal tone.(9-11) Overall,

successful cardioversion with amiodarone in general is approximately 75% within the first 24 hours.(12

Kanji and colleagues noted successful conversion to NSR was achieved in 50% of a mixed medicalsurgical patient population that underwent DCC, though 73% reverted back to AF. Successful conversion to NSR was obtained in 87% of patients receiving amiodarone, some of whom also underwent DCC, though 42% reverted back to AF at some time during their ICU stay after maintaining normal sinus rhythm for at least 24 hours after conversion. The median duration of amiodarone therapy was 4 days (range 1-49) and a median cumulative intravenous dose of 2324 mg (range 150-20550 mg).(5) Clemo and colleagues found that in a mixed ICU population, within 2 hours of amiodarone initiation, aimed at an intravenous loading dose of 2-3 mg/kg, there were significant reductions in heart rate from 150 bpm to 104 bpm and increases in systolic blood pressure from 90 mmHg to 118 mmHg. Within 24 hours, 76% of patients had successfully converted to NSR, which was maintained in 52% of patients with an average cumulative intravenous dose of 2035 ± 1962 mg and an average duration of amiodarone treatment of 84 ± 79 hours.(13) Faneil and colleagues found that in a mixed ICU setting, patients refractory to DCC or other antiarrhythmic agents, amiodarone achieved successful conversion to NSR in 80.8% of patients in an average of 171 minutes. They noted that maintenance of NSR required an average amiodarone dose of 6.9 ± 2.3 mg/kg.(14) In a recent systematic review by Kanji and colleagues, they found that no study evaluated the maintenance of conversion to NSR(6).

- 1. Rivers EP. Early and innovative interventions for severe sepsis and septic shock: taking advantage of a window of opportunity. Can Med Assoc J. 2005;173(9):1054–1065.
- 2. Christian S-A, Schorr C, Ferchau L, Jarbrink ME, Parrillo JE, Gerber DR. Clinical characteristics and outcomes of septic patients with new-onset atrial fibrillation. J Crit Care. 2008;23(4):532–536.

sure the excerpted material	Evaluate two amiodarone dosing strategies, a full loading dose versus a partial loading dose, in patients
answers the question	with new-onset AF due to severe sepsis or septic shock to assess the effect on:
	Percentage of time spent hemodynamically unstable after initiation of amiodarone infusion to
	day 7 or death
	for \ge 2 hours OR 2. HR \ge 120 for \ge 2 hours OR 3. Fluid boluses \pm vasopressors or
	dobutamine
	 Percentage of patients with conversion from atrial fibrillation to normal sinus rhythm
	 Proportion of time in atrial fibrillation vs normal sinus rhythm or other
	Mean arterial pressure (MAP)
	 Systolic blood pressure (SBP)
	Heart rate (HR)
	Vasopressor use
	Dobutamine use
	Corticosteroid use
	Concomitant rate control medication use
	Concomitant rhythm control medication or intervention use
	28-day mortality
	Intensive care unit length of stay (ICU LOS)
	Hospital LOS

Item 5 Study Population(s) Being Recruited In your recruitment plan, how many different populations of prospective subjects do you plan to target? Provide number: 1 e.g., a population can be individuals with type 2 diabetes controlled with diet and/or a population of healthy controls. Or a population can be individuals attending an education program, etc. List each different population on a separate row and provide a short descriptive label: (e.g., normal-healthy, diabetics, parents, children, etc.) To add rows use copy & paste	Identify the criteria for inclusion :	Identify the criteria for exclusion :
Patients with severe sepsis or septic shock and new onset atrial fibrillation admitted to the medical or cardiac intensive care unit	 Age ≥ 18 years New onset atrial fibrillation Severe sepsis or septic shock (defined by ≥2 systemic inflammatory response syndrome criteria + infection) 	 Age < 18 years History of atrial flutter History of atrial fibrillation QTc >500 msec at baseline 2nd or 3rd degree AV block Currently receiving anti-arrhythmic therapy Untreated thyroid dysfunction Acute or chronic hepatic failure Other indication for antiarrhythmic therapy

Recent cardiac surgery in last 30 days
Pregnancy
 Known hypersensitivity to any of the components of amiodarone , including iodine
Cardiogenic shock
Marked sinus bradycardia

Item 6

Research Plan / Description of the Research Methods *a***.** *Provide a comprehensive narrative describing the research methods. Provide the plan for data analysis* (include as applicable the *sample size calculation*).

Step-by-Step Methods:

Population: The study will be conducted at University Hospital, the 716-bed county hospital for Bexar County and serves a varied population, including patients from medically underserved areas. The patient population will come from the medical intensive care unit and the cardiac intensive care unit, a 20 and 26-bed unit, respectively, at University Hospital that is the clinical practice and teaching site for one study investigator.

Screening: Consecutive patients admitted to the medical or cardiac intensive care unit at University Hospital with new onset atrial fibrillation in the setting of severe sepsis or septic shock will be screened for study inclusion. Participants will be 18 years or older. Patients who develop new-onset atrial fibrillation in the setting of severe sepsis or septic shock will be considered for study inclusion. Exclusion criteria apply to those younger than 18 years of age, those with a history of atrial flutter, baseline QTc > 500 msec, atrial fibrillation during the index admission or in their past medical history, second or third degree AV block, those recovering from cardiac surgery done during the same hospital admission, those who have received amiodarone or other Vaughan Williams class I or III antiarrhythmic drugs in the last 6 months, untreated/poorly controlled hypothyroidism, hyperthyroidism, acute or chronic hepatic failure, other requirements of antiarrhythmic drug therapy, recent cardiac surgery in the preceding 30 days, and those who are pregnant.

Intervention: Patients aged 18 years or older who develop new-onset atrial fibrillation in the setting of severe sepsis or septic shock and in whom the medical team deems appropriate to initiate amiodarone therapy in will be considered for study inclusion. All patients will receive a 150 mg intravenous (IV) bolus dose of amiodarone, followed immediately by a continuous infusion of 1 mg/min for the first six hours, with a recommended reduction to 0.5 mg/min subsequently. Conversion from IV to oral (PO) amiodarone will occur based on patient hemodynamic stability and physician/pharmacist discretion. Patients will be randomized to receive amiodarone at a full loading dose (\geq 5g IV or \geq 10g PO +/- 20%) or a partial loading dose (<4g IV or < 8g PO). The assigned total loading dose will include all IV and PO amiodarone administered within 7 days from initiation of amiodarone. All doses will be compared in total PO amount (accounting for 50% bioavailability of PO versus IV amiodarone). The primary attending or fellow physician may over-ride randomization if the patient's amiodarone dose if the patient's severity of illness warrants a duration that differs from that assigned during randomization. In the full loading dose group, discontinuation of amiodarone will be at the discretion of the physician/pharmacists, after the pre-determined randomization loading dose has been provided.

Management Components: Facilities to be used throughout the project include the University Hospital and The University of Texas Health Science Center at San Antonio. Equipment use for direct patient care will be in keeping with standards-of-care, without any additional equipment being required for the clinical research study.

Data Collection: Data collection will include age, race, gender, BMI, data for calculating an APACHE II and SOFA scores, suspected source of infection, identified pathogens, pre-existing conditions that may predispose the patient to AF and the severity/classification of such illness (coronary artery disease, heart failure, chronic kidney disease, chronic obstructive pulmonary disease, diabetes mellitus); vital signs at the onset of AF (mean arterial pressure, systolic blood pressure, heart rate), lactate, pH, and serum bicarbonate at the time of AF onset; fluid resuscitation volume for the 24 hours prior to AF, vasopressor use (including drug, dose, duration) in the preceding 24 hours; other medications used to stabilize hemodynamic status in AF (e.g. β-blockers, calcium channel blockers, digoxin), other attempted methods of cardioversion attempted prior to amiodarone use (e.g. direct current cardioversion, other antiarrhythmic drug therapy); amiodarone loading dose, cumulative study amiodarone dose; the duration of time spent in AF before conversion to NSR, the incidence of AF recurrence; and hemodynamic variables to be assessed at various time points after the initiation of amiodarone (-6 hours, at onset of AF, 2 hours, 6 hours, 12 hours, and every 6 hours thereafter until day 7 or death)

including mean arterial pressure, central venous pressure, systolic blood pressure, heart rate, pH, serum bicarbonate, and serum lactate.

Monitoring for Efficacy and Safety:

Efficacy: Patients will be stratified based on response to therapy into one of three groups: conversion to NSR, nonconverting AF that is hemodynamically stable or non-converting AF that is hemodynamically unstable. The primary efficacy outcome is the mean heart rate every 6 hours after initiation of the amiodarone infusion to day 7 or death. Secondary efficacy endpoints will include the percentage of time spent hemodynamically unstable in the first 7 days following amiodarone initiation, intensive care unit length of stay (LOS), hospital LOS and 28-day mortality along with comparisons of the individual portions of the hemodynamic endpoints (MAP, HR, SBP), cumulative vasopressor doses of norepinephrine and vasopressin, CVP, conversion to NSR, maintenance of NSR, proportion of time spent in NSR after the start of the infusion to day 7 or death, pH, standard bicarbonate, serum lactate, and central venous oxygen saturation.

Safety: Safety outcomes include worsening of hypotension (largely related to the rate of infusion and the polysorbate 80 diluent), bradycardia, acute elevations of liver function tests ≥ 3 times the upper limit of normal, phlebitis, QTc prolongation, skin reactions, neuropathy, and pulmonary toxicity. We will also collect premature study discontinuation due to any adverse event. Because the experimental group of this study is a partial load of amiodarone, rather than a full load, it is likely that the experimental group will experience fewer amiodarone related adverse effects than those receiving the current practice. In the setting of worsening hemodynamic stability during amiodarone infusion (i.e. SBP <90 mmHg OR MAP < 70 mmHg, despite HR control of < 120 bpm; need for fluid boluses ± vasopressors or dobutamine), which the medical team believes to be caused by IV amiodarone therapy:

- 1. the amiodarone infusion rate should be decreased by 50%, with efforts to increase back to the standard infusion rate after the patient is hemodynamically stable, *or*
- 2. switch from IV amiodarone to PO amiodarone therapy at a dose of 400 mg PO TID, or
- 3. emergent electro-cardioversion at the discretion of the medical team (as is the standard of care)

Data Analysis Plan: Data will be collected and stored using Microsoft Excel or Access. After data organization and cleaning, data will be imported into JMP 12.0 or SPSS. Data will be analyzed using both descriptive and comparative statistics. The primary outcome will be analyzed using repeated measures ANOVA. Nominal and ordinal variables will be compared using Chi-square test or Fisher's Exact test, as appropriate. Continuous variables will be tested for normality using the Shapiro-Wilk W goodness of fit test. Continuous variables with normal distributions will be compared using the student's t-test, while non-parametric variables will be compared using the Wilcoxon rank sum test. Statistical significance will be defined as an alpha level less than 0.05.

All baseline demographics, including patient comorbidities, amount of fluid resuscitation, previous vasoactive therapies, and use of other interventions such as direct current cardioversion, will be entered into a multivariate regression model if the p value is less than 0.20 on univariate comparison between treatment groups. The multivariate regression model will be used to assess if baseline factors or previous treatment other than the intervention affected the study outcomes.

Based on extrapolation from available literature assessing HR control at 24 hours, we estimate that the full loading dose group will have a mean HR of 110 bpm over the course of 7 days, while the partial loading dose group will have a mean HR of 130 bpm over the course of 7 days. 7 day mean HR that is 20 bpm lower than the partial loading dose group. Therefore, we estimate that 250 patients will be necessary in each group to have an 85% power to detect a difference, assuming a 15% drop-out rate.

Item 7 Risks Section:

Complete the following table to describe the risks of all research procedures listed in Step 2, Institutional Form (items 28-34). Do not list risks of Routine care procedures here.

isks are described in the informed consent document – do not complete this table.

Research procedures	Risks
 example: History and physical Questionnaire Laboratory tests 	List the reasonably expected risks under the following categories as appropriate:
Add or delete rows as needed

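### Dobutamine, corticosteroid and rate-control drug use are outcomes with no rule for drugs already running when amiodarone starts, so a yes/no comparison would be diluted by baseline use

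*Combined protocol and SAP*

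**What the plan says.** Item 4, Secondary Outcomes, lists "Vasopressor use", "Dobutamine use", "Corticosteroid use" and "Concomitant rate control medication use" among the outcomes on which the two loading strategies are compared. None of the four carries a time window, a scale, or a rule for drugs already being given. The first secondary outcome in the same list, the percentage of time hemodynamically unstable, does have a window: from the start of the infusion to day 7 or death.

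Item 6, Data Collection, asks for "vasopressor use (including drug, dose, duration) in the preceding 24 hours". Read with the fluid item just before it, this is the period before AF onset. It also asks for "other medications used to stabilize hemodynamic status in AF", with beta-blockers, calcium channel blockers and digoxin as examples, without dividing use before amiodarone from use after it. Neither corticosteroids nor dobutamine is named there.

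Item 6, Monitoring for Efficacy and Safety, gives a quantitative vasopressor endpoint: "cumulative vasopressor doses of norepinephrine and vasopressin".

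Item 6, Data Analysis Plan, says "Nominal and ordinal variables will be compared using Chi-square test" or Fisher's exact test. Baseline factors, including earlier vasoactive drugs, enter a regression model only if the arms differ on them at p below 0.20.

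**The concern.** The patients have severe sepsis or septic shock, and no exclusion criterion names vasopressors, dobutamine, corticosteroids or rate-control drugs. Some patients can therefore be expected to be on one of these drugs when amiodarone starts. Under any-use scoring such a patient counts as a user in either arm, and the assigned load cannot change that.

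The p < 0.20 screen does not repair this. Randomisation makes balanced baseline use the expected result, so the screen would usually not be triggered, and balanced carry-over still dilutes the difference. The risk is a null result on these outcomes that cannot be interpreted: it could mean no effect of the loading dose, or a scoring rule that left little room to show one.

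**Working it through.** **The plan's own figure.** The documents give no rate, effect size or power for any drug-use outcome. The only stated figure is 250 per group for heart rate (110 vs 130 bpm, 85% power, 15% drop-out). It cannot be reproduced, because no SD is given. With 212 evaluable per arm (250 × 0.85 = 212.5) and a two-sided 5% test it implies an SD of 20 × √(212/2) / (1.960 + 1.036) ≈ 69 bpm. That has no bearing on the present point; only the 250 per arm is used below.

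**Inputs**
- From the Data Analysis Plan: n = 250 per arm and alpha 0.05. Two-sided testing is assumed, because the plan does not state it.
- Assumed: new-start rates q of 20% and 30% in patients not on the drug at initiation.
- Assumed: a share c, equal in both arms, already on the drug at initiation. It is varied from 0 to 50%.

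**Formulas**
- Any-use proportion in an arm: c + (1 − c)q. The arm difference is therefore (1 − c) × (0.30 − 0.20).
- New starts among non-users: the proportion is q, with n(1 − c) patients per arm.
- Power: Φ[(difference − 1.96 × SE₀) / SE₁], with SE₀ pooled and SE₁ unpooled.

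**Results, 250 per arm**

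| Share on drug at initiation | Any use by arm | Difference | Power, any use | Non-users per arm | Power, new starts |
|---|---|---|---|---|---|
| 0% | 20% vs 30% | 10 points | 73% | 250 | 73% |
| 10% | 28% vs 37% | 9 points | 57.5% | 225 | 69% |
| 30% | 44% vs 51% | 7 points | 35% | 175 | 58% |
| 50% | 60% vs 65% | 5 points | 21% | 125 | 45% |

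**Why new starts do better despite fewer patients.** Take c = 50%. Both methods expect the same excess of users between arms: 250 × 0.5 × 0.10 = 12.5. Under any use, the variance of that difference is about 2 × 250 × 0.625 × 0.375 = 117.2 (SD 10.8). Among non-users it is about 2 × 125 × 0.25 × 0.75 = 46.9 (SD 6.8). The carried-over users add noise and no information.

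**Sensitivity**
- With 212 per arm after drop-out and the same rates, any-use power is 66%, 51%, 30% and 18% at shares of 0, 10, 30 and 50%. New-start power is 66%, 62%, 51% and 39%.
- With assumed rates of 30% vs 45% and 212 per arm, any-use power is 89%, 59% and 38% at shares of 0, 30 and 50%. New-start power is 89%, 76% and 62%.

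The ordering is the same in each run.

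**The case against.** The best reply is that yes/no scoring is nowhere stated. The Data Analysis Plan gives a test for nominal variables but does not say that these outcomes are nominal. Data Collection itself attaches drug, dose and duration to vasopressor use, which points to a quantity. For vasopressors this largely stands: on a cumulative dose, patients already treated can still differ by arm, and carried-over dose mainly adds variance. The time-unstable outcome also counts vasopressors and dobutamine and runs from amiodarone initiation. It does not stand for corticosteroids or rate-control drugs, which have no quantitative endpoint, and only partly for dobutamine. If another scale was meant, the plan still has to name it.

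A reader might infer that carried-over use hides most of any dose effect. That needs a baseline share above 50%, and the documents give no share for any class. They also give reasons to expect lower shares for some: cardiogenic shock is excluded, the background section is cautious about beta-blockers and digoxin, and entry is defined by at least two SIRS criteria plus infection. Rhythm-control carry-over is limited, because patients on antiarrhythmic therapy are excluded.

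A reader might also infer that counting starts or dose increases in all 250 patients would restore the full 73% power. That assumes dose increases in existing users occur at the same rates as new starts in non-users, which nothing in the documents supports.

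Finally, both arms begin with the same bolus and infusion, so early new starts also occur under common treatment. New-start scoring removes carry-over, but not that source of dilution.

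**Conclusion.** The point holds as a definition gap in secondary outcomes, mainly for dobutamine, corticosteroids and rate-control drugs. If they are analysed as any use, the absolute arm difference is reduced by exactly the share on the drug at initiation. Under the assumed 20% vs 30% and 250 per arm, a 30% share takes power from 73% to 35%, whereas new-start scoring keeps 58%. These figures rest on assumed rates, an equal baseline share in the arms and an inferred yes/no scale.

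The documents do not support the wider conclusion that the trial would report no effect on hemodynamic support, since the cumulative-dose and time-unstable endpoints address that separately. Randomisation keeps the comparison unbiased and the primary heart-rate result is unaffected. This is a low-cost improvement, not a threat to the trial.

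**What to change.** 1. Add to Data Collection, for each of vasopressors, dobutamine, corticosteroids and rate-control drugs, the status at amiodarone initiation, with dose where applicable. Report it as a baseline characteristic.
2. In Item 4, define the dobutamine, corticosteroid and rate-control outcomes as a new start between initiation and day 7 or death, among patients not on that drug at initiation, compared between randomised arms.
3. State that the vasopressor outcome in Item 4 is the cumulative norepinephrine and vasopressin dose already named in Item 6, counted from amiodarone initiation and adjusted for the vasopressor dose at initiation whatever the baseline p-value.

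The cost is one field per drug from the medication record and a smaller denominator for the new-start outcomes (for example 125 rather than 250 per arm at a 50% baseline share). New-start scoring also leaves out dose escalation in patients already treated. No extra patients or procedures are needed.

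### No reading is scheduled when amiodarone starts, although the heart-rate and sinus-rhythm outcomes are counted from that moment

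*Combined protocol and SAP*

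**What the plan says.** All references are to the combined protocol and SAP.

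- **Reading times** (Item 6, Data Collection): "hemodynamic variables to be assessed at various time points after the initiation of amiodarone (-6 hours, at onset of AF, 2 hours, 6 hours", continuing "12 hours, and every 6 hours thereafter until day 7 or death". The listed variables are MAP, CVP, SBP, heart rate, pH, bicarbonate and lactate.
- **Separate baseline** (same paragraph): "vital signs at the onset of AF (mean arterial pressure, systolic blood pressure, heart rate". Lactate, pH and bicarbonate are also tied to AF onset.
- **Earlier treatment** (same paragraph): the plan records "other attempted methods of cardioversion attempted prior to amiodarone use (e.g. direct current cardioversion, other antiarrhythmic drug therapy". It also records "other medications used to stabilize hemodynamic status in AF (e.g. β-blockers, calcium channel blockers, digoxin", without saying when these were given.
- **Outcome clock** (Item 6, Monitoring for Efficacy and Safety): "The primary efficacy outcome is the mean heart rate every 6 hours after initiation of the amiodarone infusion to day 7 or death". A secondary outcome is "proportion of time spent in NSR after the start of the infusion to day 7 or death".
- **Conversion** (Item 4, Secondary Outcomes): the percentage of patients going from AF to sinus rhythm. No start time is given, and AF at amiodarone start is not required.
- **Analysis** (Item 6, Data Analysis Plan): repeated measures ANOVA for the primary outcome, with no baseline heart-rate covariate named. Prior vasoactive treatment and cardioversion enter a regression only if they differ between arms at p < 0.20.

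**The concern.** The outcomes start at amiodarone initiation, but the last pre-treatment reading with a stated anchor is at AF onset, which is a different event. The plan itself allows for cardioversion attempts between the two. For a patient treated in that interval, the AF-onset heart rate, blood pressure and rhythm may not be those present when amiodarone begins.

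Three things depend on the missing values:

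1. **Primary outcome.** Heart rate at amiodarone start is the natural covariate for later heart rate, and it is not scheduled.
2. **Conversion and the response-to-therapy groups.** A patient already back in sinus rhythm at the bolus could be counted as a conversion, because the outcome has no start time.
3. **Safety.** Worsening hypotension is a listed safety outcome. Judging whether blood pressure worsened on amiodarone needs a blood pressure from when it started.

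**Working it through.** **1. Schedule against outcome clock.** Post-initiation readings fall at 2 hours and at 6, 12, …, 168 hours. That is 168 / 6 = 28 readings on the six-hour grid plus one at 2 hours, 29 in all. Two earlier readings are listed: minus six hours (anchor not stated) and AF onset. Readings at amiodarone start: 0.

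**2. Patients possibly in sinus rhythm before amiodarone.** Inputs:

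- Share with prior cardioversion, p: 10–20%. This is an assumption; the documents give no figure.
- Success: 50%, from Item 3 ("successful conversion to NSR was achieved in 50% of a mixed medicalsurgical patient population that underwent DCC").
- Reversion to AF: 73%, from the same sentence of Item 3, read as a share of those converted. Its timing relative to amiodarone is not given.

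Share already in sinus rhythm, f = p × 0.50 × (1 − share reverting before amiodarone):

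| Prior cardioversion | No reversion before amiodarone | All 73% revert before amiodarone |
|---|---|---|
| 10% | 0.10 × 0.50 = 5% | 0.10 × 0.50 × 0.27 = 1.35% |
| 20% | 0.20 × 0.50 = 10% | 0.20 × 0.50 × 0.27 = 2.7% |

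The range is about 1.4–10% of patients. With 250 per group, that is 250 × 0.0135 ≈ 3 to 250 × 0.10 = 25 patients per group.

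**3. Effect on the reported conversion rate.** If a proportion c of the remaining patients convert, the reported rate is f + (1 − f)c. The excess over c is f(1 − c), which cannot exceed f. With c = 0.75 (the general 24-hour amiodarone figure in Item 3), the excess is 0.0135 × 0.25 = 0.3 to 0.10 × 0.25 = 2.5 percentage points. A lower c gives a larger excess.

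**4. Precision of the primary outcome.** Adjusting for a baseline that correlates r with later mean heart rate removes r² of the outcome variance. The correlations are assumed:

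- AF-onset heart rate, r = 0.2–0.4: 0.04–0.16, or 4–16%.
- Heart rate at amiodarone start, r = 0.4–0.6: 0.16–0.36, or 16–36%.

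The plan names neither as a covariate, so at present it gains nothing from either.

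**5. Does carry-over tilt the arms?** Suppose prior treatment in a fraction p of patients shifts heart rate by e bpm, with 250 × 0.85 ≈ 212 evaluable per arm. Under randomization the expected arm difference is 0, and its chance SD is e × √(2p(1 − p)/212).

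- p = 0.10, e = 10: 10 × √(0.18/212) = 0.29 bpm.
- p = 0.50, e = 20: 20 × √(0.50/212) = 0.97 bpm.

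The planned difference is 130 − 110 = 20 bpm.

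**6. Does the planned adjustment fill the gap?** Under randomization, a p < 0.20 screen admits a given baseline variable about one time in five, so prior cardioversion would usually stay out of the model. Even when admitted, the fact that cardioversion was tried does not give the heart rate, blood pressure or rhythm at amiodarone start.

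**The case against.** Much of the opposing case stands, and it limits what can be claimed.

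- **Bias between arms.** A reader might infer that earlier treatment biases the comparison. The documents do not support this: patients are randomized, both arms begin with the same bolus and infusion, and no outcome is defined as change from baseline.
- **The 2-hour reading.** A reader might infer that it could be timed from AF onset. The sentence introduces the readings as following amiodarone initiation, so 2 hours naturally counts from there. Only the minus-six-hour reading lacks an anchor.
- **Both early readings precede other treatment.** This is safe only for the AF-onset reading. If minus six hours counts from amiodarone and AF began earlier, it may fall after other treatment.
- **Rate-control drugs.** These might be taken as given before amiodarone, but they are undated. Only cardioversion attempts are placed before it, and the exclusions for current antiarrhythmic therapy (Item 5) and class I or III drugs in the last 6 months (Item 6, Screening) narrow the drug route.
- **Early conversions certainly count, or rhythm goes unrecorded.** Neither is established. Grouping by response to therapy suggests otherwise, time in sinus rhythm cannot be computed without rhythm from the start, and time in AF and recurrence are collected separately. The firm point is that conversion has no defined start.
- **Precision may not be scarce.** The plan states no SD, so its 250 per group cannot be reproduced. Solving back (two-sided 0.05) gives 20 × √(212.5/2) / (1.960 + 1.036) = 68.8 bpm. With assumed SDs of 20–30 bpm, 2 × SD² × 2.996² / 20² gives 18–41, or 22–49 per arm after dividing by 0.85. Better precision is then a gain, not a rescue.

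The objection does not remove the central fact: the schedule, followed exactly, yields no reading at the moment from which the outcomes are counted.

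**Conclusion.** The point holds as an inexpensive improvement, not as a threat to the validity of the randomized comparison. No reading is scheduled at amiodarone start, the minus-six-hour reading has no anchor, and conversion has no start time. The AF-onset reading may therefore misstate the patient's condition when amiodarone begins.

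About 1.4–10% of patients could count as converted before treatment. This assumes that 10–20% have prior cardioversion and depends on how many of the cited 73% revert first. The excess in the reported rate would be smaller than that share. The precision forgone on the primary outcome rests wholly on assumed correlations. The loss for attributing response and worsening hypotension to amiodarone is qualitative; the documents give nothing from which to size it. The screened adjustment in the Data Analysis Plan does not supply the missing values.

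**What to change.** - **Item 6, Data Collection:** define time zero as the start of the amiodarone bolus for all later readings, state what minus six hours is counted from, and add heart rate, MAP, SBP and rhythm at time zero from the ICU chart. Keep the AF-onset values as descriptors of the episode.
- **Item 6, Data Analysis Plan:** pre-specify time-zero heart rate as a covariate in the primary repeated-measures analysis, whether or not the arms differ on it.
- **Item 4 and Item 6, conversion outcome:** compare conversion among patients in AF at time zero. Both arms share the initial bolus and infusion, so this restriction uses a value fixed before assigned treatment differs. The documents do not say whether randomization precedes the bolus and describe no blinding, so the order should be stated too.

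**Cost:** one extra row of routinely charted data and a few sentences of wording. Patients in sinus rhythm at time zero leave the conversion denominator, roughly 3 to 25 per group under the assumptions above. They remain in the primary analysis. No dose or clinical rule changes.
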